**Moderating Variables will be assessed only at Baseline ( $T_0$ ) through:**

Moderating variables will be collected using the following instruments: a 9-item socio-demographic questionnaire (NHANES III, CDC), a 10-item common chronic health condition for adults 65+ questionnaire (adapted from the Nation Council on Aging(NCOA), a 12-item self-reported measures of current oral disease / tissue damage questionnaire (Gilbert et al., 1997), and a 5-item oral hygiene (adapted from Kuusela, 1997 and WHO) These measures will be considered as potential moderators and will be collected at the baseline visit only.

**Table 8.1.2. Qualitative Focus Study Procedures / Evaluations (to be conducted in year 2, year 3, and year 4 either virtually or at a convenient housing facility, based on housing site circumstances at the time of focus group scheduling)**

Subject	Planning / Design	At the Focus Group Process	Data Collection
Group Participants	
Recruitment
 
 
Participants who will complete the clinical trial randomly invited to one of the three focus group interviews
 
	
Comfortable environment
 
 
Provide signed and dated consent form at the beginning of interview protocol
 
	
Activities
 
 
Generate ideas / efforts to contribution
 
Engagement and input on focus group activity
 

Moderator	
Design for group interview
 
 
Develop an agenda and discussion guide
 
Review participants' demographics and characteristics
 
Finalize / review a protocol design with the study staff
 
	
Probing with Semi-structured questionnaire
 
 
Opening
 
Introduction
 
Transition
 
Key questions
 
Conclude (Breen, 2007)
 
 
Data collection
 
 
Audio recording
 
Summary notes
 
	
Key topics
 
 
Inquire as to participants' levels of satisfaction in accessibility and practices of a received intervention (Robinson et al., 2005)
 
Dissemination of the treatment of SDF or ART+FV to other older populations
 
Barriers experienced in getting treatment of SDF or ART + FV (Newton et al., 2001)
 
Resources and challenges in seeking dental care (adapted from Gussy et al., 2006)
 

Study Staff	
Define methodologies
 
 
Define a purpose and goal
 
	
Process
 
 
Observational notes
 
	
Data Analysis
 
 
Transcription of audio tapes
 

	

• Scheduling meeting

• Guidelines for recruiting (non-proportional approach)

• Book a room for an interview

• Arrange materials (name tags, chairs, and table)

	

• Capture of non-verbal activities

 
Acknowledgment
 

• Refreshments

• Gift card (\$25) / travel cost

	

• Data coding / organizing information by using Atlas.ti software

--	--	--	---

### **8.1.2 Focus Group Study Procedures / Evaluations**

Focus groups will be led by an experienced moderator trained in qualitative interviewing techniques. The moderator will use a semi-structured interview guide to gather a large number of opinions and engage in a collective brainstorming of ideas and solutions.

Focus group discussions are a part of qualitative technique wherein a researcher assembles a group of individuals to discuss a specific topic that can provide a deeper understanding of or insight into a particular issue. We will use the phenomenological approach and ground theory to focus group research for the current study.

#### **Recruitment, planning and development of the discussion guide**

- *Participant recruitment* will occur prior to the focus group meeting. The research team will contact individual participants to promote participation for the focus group study via phone, e-mail, and in-person. We will randomly invite participants that have successfully completed the clinical trial until 30 participants from the 22 housing facilities agree to participate in one three focus group discussion (non-proportional sampling).
- *The moderator* will prepare a focus group guide for each discussion. The moderator will outline the flow of questions and topics to be covered. This discussion strategy will encourage participants to pursue topics of interest and to reveal experiences regarding the treatment.
- *The research staff* will develop and agree on standard practice for focus group discussion. In collaboration with the moderator, the research team will establish management guidelines for the focus group meeting that enable the moderator to effectively capture key phrase and understand group dynamics. The staff will reserve a convenient and accessible venue and prepare necessary materials for interview. Arrangements will be made for name tags, food, and drinks for participants. An honorarium (\$25) will be given to each participant in appreciation of their time as well as any travel costs.

#### **Focus group procedures and data collection**

*The focus groups will be conducted either virtually or at a convenient housing facility, based on housing site circumstances at the time of focus group. Each focus group participant will have provided a signed and dated consent form prior to the beginning of the group discussion. The moderator will encourage active participation in interviews to gain valuable inputs and ideas.*

- *The moderator will be responsible for initiating the discussion and keeping the group on task as well as creating a comfortable, relaxed atmosphere. Focus group sessions will be approximately 90 minutes and an audio recording will be also made so as to ensure a complete record of what was discussed.*
- *The moderator will conduct each focus group using a semi-structured interview guide based on five categories of questions (opening, introduction, transition, key, and ending). The interview guide for participants will focus on levels of satisfaction of the treatment (SDF or ART + FV) in terms of accessibility and convenient practices; barriers and facilitators experienced while receiving treatment procedures of SDF or ART +FV; resources and challenges of the treatment of SDF or ART + FV; a potential in dissemination of the treatment of SDF or ART + FV to other populations of older adults. The interview discussion will be audio-recorded, and this data will foster an in-depth understanding of participants' perceptions and attitudes toward the conducted interventions.*
- *One or two staff members who have been trained in focus group interviews will attend the discussion to record non-verbal cues, signals, and facial expressions. Observational notes during the interview and summary notes after the interview will also be recorded by the study staff. After each focus group, in discussion with the moderator, the study staff will debrief on key concepts and identify any new questions that should be added to the next focus group, if needed. Focus group data collected with two approaches of a group interview and observational approaches will be transcribed into data coding steps. The coded data will be analyzed using Atlas.ti software, which helps to integrate interview findings into coherent qualitative study results.*

## 9 ASSESSMENT OF SAFETY

### 9.1 Specification of Safety Parameters

This study involves administration of two FDA approved devices, which are applied using approved standardized protocols for administration (SDF, ART+FV).

#### 9.1.1 *Unanticipated Problems*

Unanticipated problems involving risks to subjects or others to include, in general, any incident, experience, or outcome that meets **all** of the following criteria:

- unexpected in terms of nature, severity, or frequency given (a) the research procedures that are described in the protocol-related documents, such as the IRB-approved research protocol and informed consent document; and (b) the characteristics of the subject population being studied;
- related or possibly related to participation in the research (“possibly related” means there is a reasonable possibility that the incident, experience, or outcome may have been caused by the procedures involved in the research); and
- suggests that the research places subjects or others at a greater risk of harm (including physical, psychological, economic, or social harm) than was previously known or recognized.

The primary responsibility for the evaluation of unanticipated problems lies with the PI of the protocol. This includes the documentation, investigation, and follow-up of these events. Consistent with CWRU IRB policy, the PI will report these events to the IRB within three (3) business days of discovery of the problem or event.

The PI must complete the Unanticipated Problems, Deviations, Adverse Events Form and submit it to the IRB. If the Unanticipated Problem does not meet these criteria, then the event does not meet reporting criteria and should be retained in the investigator's file for reference.

#### 9.1.2 *Adverse Events*

An adverse event (AE) is any unintended negative experience associated with the study materials or research procedures. Adverse events include both physical and psychological harms.

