#### 9.1.3 *Serious Adverse Events*

A serious adverse event (SAE) is any adverse event that results in one or more of the following outcomes:

- Death
- A life-threatening event
- Inpatient hospitalization or prolongation of existing hospitalization
- A persistent or significant disability/incapacity
- A congenital anomaly or birth defect
- An important medical event based upon appropriate medical judgment

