## 9.2 Time Period and Frequency for Event Assessment and Follow-Up

The primary responsibility for the evaluation of these events lies with the PI of the protocol. This includes the documentation, investigation, and follow-up of these events. For those events that require reports to the IRB, it is the PI's responsibility to submit the reports in a timely manner. If new risks to the participants are identified they must be included in a revised consent form.

Multiple factors determine if an Unanticipated Problems, Deviations, Adverse Events Form is required. One of the most important distinctions is whether the event is expected or unexpected. To make this determination, it is necessary to know the underlying condition of the subject including co-morbidities, and the severity and frequency of events in participants who qualify for the study. An expected adverse event meets one or more of the following criteria:

- Attributed to the underlying condition of the participant being studied.
- Attributed to the subject population being studied.
- Identified in the literature, investigator brochure, other risk documentation or informed consent.

An unexpected adverse event meets one or more of the following criteria:

- Not listed in the informed consent, protocol, or other study documents.
- Not attributed to the underlying condition of the subject taking into account co-morbid conditions.
- Not attributed to the subject population
- Severity and/or frequency of the event are beyond the range previously known.

Unanticipated problems will be recorded in the data collection system throughout the study.

Study staff will *administer the Safety Questionnaire (Pre-exam) prior to the dental exam and treatment and then contact each participant by phone 24-72 hours following treatment receipt to administer the Safety Questionnaire by phone*. The PI, and co-investigator, [name], will review

all records of participants who indicate they needed medical care or experienced symptoms since the treatment on a weekly basis to determine the severity and its relation to the treatment. Proper notifications will then be made to the IRB, PCORI and the DSMB based on their evaluation. Events will be followed for outcome information until resolution or stabilization. The PI will record all reportable events though the duration of the study.

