### **9.3 Characteristics of an Adverse Event**

#### ***9.3.1 Relationship to Study Intervention***

To assess relationship of an event to study intervention, the following guidelines are used:

1. Related (Possible, Probable, Definite)
  - a. The event is known to occur with the study intervention.
  - b. There is a temporal relationship between the intervention and event onset.
  - c. The event abates when the intervention is discontinued.
  - d. The event reappears upon a re-challenge with the intervention.
2. Not Related (Unlikely, Not Related)
  - a. There is no temporal relationship between the intervention and event onset.
  - b. An alternate etiology has been established.

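### The adverse event definition in 9.1.2 already requires association with the study, which contradicts 9.2, 9.3.1 and 9.4 and leaves a hospitalisation judged unassociated with no stated SAE route

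*Combined protocol and SAP*

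**What the plan says.** Section 9.1.2 defines the basic unit of safety recording: "An adverse event (AE) is any unintended negative experience associated with the study materials or research procedures". Section 9.1.3 builds on it: "A serious adverse event (SAE) is any adverse event that results in one or more of the following outcomes". Its list of outcomes includes death and inpatient hospitalisation.

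Section 9.2 describes the workflow. Staff give a Safety Questionnaire before each exam and telephone the participant after treatment. The PI and a co-investigator then review "all records of participants who indicate they needed medical care or experienced symptoms since the treatment on a weekly basis", and do so "to determine the severity and its relation to the treatment". After that, "Proper notifications will then be made to the IRB, PCORI and the DSMB based on their evaluation". The same section lists what makes an adverse event expected. One criterion is "Attributed to the underlying condition of the participant being studied".

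Section 9.3.1 sets out a separate relatedness step: "To assess relationship of an event to study intervention, the following guidelines are used". One of its two classes is "Not Related (Unlikely, Not Related)".

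Section 9.4.1 sends deaths judged unrelated to the IRB at the next Continuing Review, and all SAEs as soon as the PI learns of them. Section 9.4.2 first requires every adverse event that meets the SAE criteria to go to PCORI, then gives timelines that refer only to study-related deaths and study-related SAEs.

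**The concern.** Safety reporting normally has two steps: record every untoward event, then judge whether it is related. Section 9.1.2 puts part of the second step into the first. If an event must be associated with the study before it counts as an adverse event, one judged unassociated is not an adverse event, and under 9.1.3 it cannot be an SAE however serious it is.

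This matters in this population. The Protocol Summary expects a mean age of 74 and 83% with two or more medical conditions, so hospital stays with no obvious link to a dental procedure are to be expected. Comparing such events between arms regardless of attribution is how an unexpected excess would be noticed. Section 9.5 plans no halting rules and relies on DSMB review, so the content of the SAE tables carries weight.

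**Working it through.** No arithmetic applies. The plan gives no figure to reproduce and no background rate of hospitalisation or death. The check is to set the sections side by side and follow three events through them.

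**Consistency of the sections**

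- 9.1.2 against 9.3.1: if every adverse event is associated with the study, the Not Related class has almost nothing to classify.
- 9.1.2 against 9.2: an event ascribed to the participant's own illness can be an expected adverse event under 9.2, but hardly fits a definition that requires association with study materials or procedures.
- 9.1.3 against 9.4.2: limiting the PCORI timelines to study-related SAEs is redundant if every SAE is already associated. The qualifier makes sense only if SAEs can be unrelated.
- 9.1.2 against 9.4.1: the rule for unrelated deaths assumes such deaths are tracked, but does not say they are SAEs.

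**Three events followed literally**

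1. A hospitalisation judged associated is an adverse event (9.1.2) and an SAE (9.1.3), and is reported under 9.4.1 and 9.4.2. There is no difficulty.
2. A death judged unassociated is not an adverse event, and so not an SAE. It still reaches the IRB at Continuing Review (9.4.1), but has no clear place on the SAE form to PCORI.
3. A hospitalisation judged unassociated is likewise neither an adverse event nor an SAE. Section 9.4.1 has no counterpart to the rule for unrelated deaths, so no SAE route is stated.

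**Whether other recording duties close the gap**

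Section 9.2 requires unanticipated problems to be recorded in the data system, but 9.1.1 limits these to events related or possibly related to the research. Section 9.2 also has the PI record reportable events, and what is reportable depends on the definitions at issue. The questionnaire is wider, since it picks up symptoms and medical care whatever the cause. Between visits, however, it depends on the participant being present for the next pre-exam questionnaire (weeks 26 and 52 in Appendix A). Section 7.4 ends data collection for those who withdraw or move away.

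**Who judges**

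Section 9.2 gives attribution to the PI and a co-investigator. Allocation is by facility (5.4.1), section 6.10 says the products are not masked, and 5.4.2 discusses masking only of participants and hygienists. No masking of the two safety reviewers is described, though their status is not stated either way.

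**The case against.** The strongest reply is that section 9 as a whole shows what is meant. Sections 9.2, 9.3.1 and 9.4 all treat unrelated events as adverse events or SAEs, so association in 9.1.2 could be read loosely, for instance as a link in time. This has force, and it is why the finding is a contradiction and not a proven loss of events. It does not remove the problem. Section 9.3.1 uses a temporal relationship as one of its own tests and its absence as a ground for Not Related, so a temporal reading of 9.1.2 still duplicates that step and excludes part of that class. Two people could code the same hospital stay differently and both follow the protocol.

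A reader might infer several stronger things that the documents do not support:

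- *Events are screened out before relatedness is assessed.* No such step is described. Section 9.2 reviews all reports of symptoms or medical care and attributes once, at that review.
- *Unrelated deaths are lost.* Section 9.4.1 sends them to the IRB, although later.
- *The adverse event frequency in Table 8.1.1 is not comparable between arms.* Its source is the Safety Questionnaire, given on a fixed schedule in both arms (8.1.1). Nothing says that count is screened by 9.1.2.
- *The DSMB cannot see an excess.* Section 9.5 promises it the safety data in full, and 5.5.2 adds the reasons for withdrawal. What is not stated is whether the tables will count serious events regardless of relatedness.
- *Different staff in each arm would attribute at different rates.* The same two reviewers serve both arms, so an illustration built on arm-specific staff would not fit this protocol. A reviewer who knows the arm could still be influenced by it.

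It is also fair to say that the materials are FDA-cleared and in current use (6.1), and that safety is a process outcome. Both limit the stakes.

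**Conclusion.** Wrong as written: the definition in 9.1.2, inherited by 9.1.3, contradicts 9.2, 9.3.1 and 9.4. Taken literally, it makes the recording and reporting of a serious event as an SAE depend on attribution, above all for hospitalisations. SAE counts by arm may then reflect the judgement of reviewers for whom no masking is described.

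The finding concerns the definition and onward SAE reporting, not initial capture. It rests on a literal reading of 9.1.2, and, for possible bias between arms, on the inference that the reviewers know the allocation. No numerical size can be given, because the documents contain neither a background rate of serious events nor any indication of how often events would be judged unassociated.

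**What to change.** 1. In 9.1.2, define an adverse event as any untoward event after first study treatment, whether or not it is considered associated with study materials or procedures. Section 9.1.3 can then stand unchanged.
2. State that the relatedness assessment in 9.3.1 is applied afterwards, to every recorded event.
3. Reconcile 9.1.2, 9.1.3, 9.2, 9.3.1, 9.4.1 and 9.4.2. In particular, say for each recipient whether the reporting rule covers all SAEs or only related ones, and where an unrelated hospitalisation is recorded.
4. For the DSMB, tabulate serious events by arm twice: regardless of relatedness, and for related events only. Count deaths and hospitalisations in the first table whatever their attributed cause.

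The definition itself takes one sentence. The remaining cost is the cross-reference edits, IRB approval of the amendment (14.2), and more event forms for hospital stays and deaths that will mostly be judged unrelated.

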#### 9.1.3 *Serious Adverse Events*

A serious adverse event (SAE) is any adverse event that results in one or more of the following outcomes:

- Death
- A life-threatening event
- Inpatient hospitalization or prolongation of existing hospitalization
- A persistent or significant disability/incapacity
- A congenital anomaly or birth defect
- An important medical event based upon appropriate medical judgment

## 9.2 Time Period and Frequency for Event Assessment and Follow-Up

The primary responsibility for the evaluation of these events lies with the PI of the protocol. This includes the documentation, investigation, and follow-up of these events. For those events that require reports to the IRB, it is the PI's responsibility to submit the reports in a timely manner. If new risks to the participants are identified they must be included in a revised consent form.

Multiple factors determine if an Unanticipated Problems, Deviations, Adverse Events Form is required. One of the most important distinctions is whether the event is expected or unexpected. To make this determination, it is necessary to know the underlying condition of the subject including co-morbidities, and the severity and frequency of events in participants who qualify for the study. An expected adverse event meets one or more of the following criteria:

- Attributed to the underlying condition of the participant being studied.
- Attributed to the subject population being studied.
- Identified in the literature, investigator brochure, other risk documentation or informed consent.

An unexpected adverse event meets one or more of the following criteria:

- Not listed in the informed consent, protocol, or other study documents.
- Not attributed to the underlying condition of the subject taking into account co-morbid conditions.
- Not attributed to the subject population
- Severity and/or frequency of the event are beyond the range previously known.

Unanticipated problems will be recorded in the data collection system throughout the study.

Study staff will *administer the Safety Questionnaire (Pre-exam) prior to the dental exam and treatment and then contact each participant by phone 24-72 hours following treatment receipt to administer the Safety Questionnaire by phone*. The PI, and co-investigator, [name], will review

all records of participants who indicate they needed medical care or experienced symptoms since the treatment on a weekly basis to determine the severity and its relation to the treatment. Proper notifications will then be made to the IRB, PCORI and the DSMB based on their evaluation. Events will be followed for outcome information until resolution or stabilization. The PI will record all reportable events though the duration of the study.

The PI must complete the Unanticipated Problems, Deviations, Adverse Events Form and submit it to the IRB. If the Unanticipated Problem does not meet these criteria, then the event does not meet reporting criteria and should be retained in the investigator'

